In context of these multivariable logistic or linear regression analyses, first univariate logistic or linear regressions will be performed. Afterwards, all covariates which were significant at the p-level of 0.2 in the univariate analysis will be entered into a backward selection multivariable logistic or linear regression. While the treatment variable will be kept in the model, backwards elimination will be used to remove covariates until p-values of all remaining covariates are <0.05 (based on Type III analysis of effects).

The analysis will be done for all ten datasets resulting from multiple imputation, respectively. However the results will be shown in an aggregated way.

The variables used for regression are the same as for propensity score matching:

- age at registration [continuous variable]
- age at registration squared [continuous variable]
- sex [male / female]
- baseline CAT™ [continuous variable]
- baseline mMRC [mMRC-grade 0 / mMRC-grade I / mMRC-grade II / mMRC-grade III / mMRC-grade IV]
- exacerbation history [yes: at least 1 exacerbation requiring hospitalization or at least 2 moderate exacerbations / no: no exacerbations or only mild exacerbations]
- pack-years of smoking [continuous variable]
- FEV1 [no finding / < 30% / 30% - 49% / 50% - 79% / ≥ 80%]
- Logarithm of eosinophil levels [continuous variable]
- Specialization of attending physician [GP/ pulmonologist/ internal specialist]

For each categorical variable the class with the highest frequency will be chosen as reference value, respectively.

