9.7.1 Main analysis

For the two primary outcomes, as specified in section 9.3.2.1, the comparative treatment effect will be estimated along with 95% confidence intervals.

The estimation of the treatment effect is subject to potential confounding. Therefore, adjusted analyses are required. Multiple analytical approaches will be applied to allow an assessment of the sensitivity of the results to these approaches:

- Propensity score matching (primary analysis; requires data to be discarded from the analysis)

[figure not shown]
Proprietary confidential information © 2019 Boehringer Ingelheim International GmbH or one or more of its affiliated companies

- Propensity score weighting (uses the complete data set)
- Multivariable regression modeling (uses the complete data set)

Multiple imputation will be applied to estimate the propensity score model and the multivariable regression models.

Covariates for adjustment include patient demographics (age, sex), disease characteristics (baseline CATTM / mMRC, exacerbation history, pack-years of smoking, FEV₁, eosinophil levels) and health care provider (GP / pulmonologist). Baseline comparability before and after matching will be assessed using standardized differences.

The comparative effectiveness on the primary endpoints will be determined based on model coefficients (along with 95% confidence intervals) and statistical testing of these coefficients. Since the study is exploratory in nature, no multiplicity adjustment is planned.

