7.3 PRIMARY ENDPOINTS

The primary outcomes are reported in a descriptive manner, will be compared in an explorative manner and are not safety outcomes. For the three primary outcomes the comparative treatment effect will be estimated along with 95% confidence intervals (CI).

For absolute changes in total mMRC and CATTM score between baseline and end of observation, summary statistics will be provided. Furthermore linear regression will be used to analyse the change in mMRC and CATTM score. The model will adjust for clustering (matched patients) using generalized estimating equations (GEEs) and take the respective baseline variable as covariate into account.

In an additional analysis it will be investigated if the therapy effect is heterogeneous with respect to the GOLD spirometric classification and the GOLD patient group, respectively. The stratified estimators with their corresponding 95% confidence interval will be shown. If

appropriate, a p-value of the interaction of treatment and GOLD may be provided. If some of the strata are too small they will be omitted from the analysis. **mMRC and CAT™ score**

The mMRC Dyspnea Scale consists only of one question on symptom severity and yields a score of either 0, 1, 2, 3 or 4.

The total CAT™ score ranges from 0 to 40. A higher score is indicative of worse status. According to the manual missing values will not be imputed, no total score will be calculated if at least one item is missing. However a single imputation will be done as sensitivity analysis, by imputing the response for the missing question as mean of the other questions of the respective patient.

The total CAT™ score and the corresponding subscales are calculated as follows, in case that answers to all 8 items are available:

$$\text{Total CAT}^{\text{TM}} \text{ score} = \sum_{i=1}^8 \text{item}_i$$

The estimation of the treatment effect is subject to potential confounding. Therefore, beside the analysis based on data as collected adjusted analyses are required. Multiple analytical approaches will be applied to allow an assessment of the sensitivity of the results to these approaches:

- Propensity score matching (primary analysis; requires data to be discarded from the analysis)
- Propensity score weighting (uses the complete data set)
- Multivariable regression modeling (uses the complete data set)

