Ten multiple imputations will be applied to estimate the propensity score model and the multivariable regression models. The average of the propensity scores will be used to analyze the treatment effect.

Propensity score matching:

Estimation of propensity scores will be realized via multivariable logistic regression, modelling treatment dependent on several matching variables.

Variables used for propensity score estimation are:

- age at registration [continuous variable]
- age at registration squared [continuous variable]
- sex [male / female]
- baseline CAT™ [continuous variable]
- baseline mMRC [mMRC-grade 0 / mMRC-grade I / mMRC-grade II / mMRC-grade III / mMRC-grade IV]
- exacerbation history [yes: at least 1 exacerbation requiring hospitalization or at least 2 moderate exacerbations / no: no exacerbations or only mild exacerbations]

- pack-years of smoking [continuous variable]
- FEV1 [no finding / < 30% / 30% - 49% / 50% - 79% / ≥ 80%]
- Logarithm of eosinophil levels [continuous variable]
- Specialization of attending physician [GP/ pulmonologist/ internal specialist]

If the propensity score model can be fitted without convergence problems, no further variable selection will be performed. In case of convergence problems, variables causing failed convergence will be eliminated from the model.

Density curves of the propensity score distribution stratified by treatment group will be shown to assess overlap.

Matching based on the propensity score is realized using a (greedy) nearest-neighbor matching on the logit of the propensity score with a caliper of 0.2 standard deviations of the logit of the PS.

Matching of patients treated with Spiolto® Respimat® to patients treated with triple combination (free or fixed LAMA + LABA + ICS) will be implemented using PROC PSMATCH with a random order of treated patients to be matched. It will be started with a 1:1 matching, but if the balance can be kept a 1_{Triple}:2_{Spiolto} or even 1_{Triple}:3_{Spiolto} matching will be performed.

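### Low-priority, cheap improvement: the sensitivity regression selects confounders by p-value, so it need not adjust for the same covariates as the propensity score model it is compared with

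*SAP*

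**What the plan says.** Protocol 9.7.1 gives one adjustment list: "Covariates for adjustment include patient demographics (age, sex), disease characteristics" (baseline scores, exacerbation history, pack-years, FEV1, eosinophils) and type of health care provider. It mentions no selection by p-value, and Protocol 9.7 leaves details to the SAP.

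SAP 7.3 runs matching (primary), weighting and multivariable regression for a stated purpose: "Multiple analytical approaches will be applied to allow an assessment of the sensitivity of the results to these approaches". For the propensity score, "If the propensity score model can be fitted without convergence problems, no further variable selection will be performed".

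For the regression, SAP 7.3 says "The variables used for regression are the same as for propensity score matching" and lists ten terms. Before that list, however, it sets a univariate screen: "all covariates which were significant at the p-level of 0.2 in the univariate analysis will be entered into a backward selection". It continues: "While the treatment variable will be kept in the model, backwards elimination will be used to remove covariates" until each one left has p<0.05. On imputation: "The analysis will be done for all ten datasets resulting from multiple imputation, respectively. However the results will be shown in an aggregated way". No rule is given for ten models that hold different covariates.

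**The concern.** The two lists are the same only as candidates. The fitted sets coincide only if every term passes both p-value steps. Only treatment is forced, so even the baseline score is not kept by rule, although the GEE model for matched patients in the same section includes it by design.

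Both steps look only at association with the outcome. Confounding depends on the association with treatment as well, and treatment here is the physician's choice. A covariate that strongly drives that choice but predicts the outcome weakly is the kind that selection tends to drop. The interval from the selected model also takes no account of the selection.

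At stake is how the sensitivity comparison can be read. If the regression and the matched analysis disagree, part of the difference may come from the selection rule and not from the method.

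**Working it through.** **1. Patients available.** The plan's sample size reproduces. CAT margin 2, SD 7, one-sided 2.5% and 90% power (Protocol 9.5.1) give 259 per group with an exact t calculation; 259/0.6 = 431.7, so 432 per group and 864 in total. The regression loses no patients to matching, so only the 10% drop-out applies: 864 x 0.9 = 777.6, or 778.

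**2. Can the full list be fitted?** Degrees of freedom: age 1, age squared 1, sex 1, CAT 1, mMRC 4, exacerbation history 1, pack-years 1, FEV1 4, log eosinophils 1, specialty 2. The sum is 17, or 18 with treatment. 778/18 = 43 patients per parameter, so sparse data do not call for selection. Loss of degrees of freedom alone raises the SE by the factor sqrt(776/759) = 1.011.

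**3. What selection leaves behind (hand check).** Take a covariate with true effect b CAT points per SD. Its estimate has SE s = 7/sqrt(778) = 0.251, and it is dropped if the estimate lies within c = 1.96 x 0.251 = 0.492 of zero. The share of its confounding left in the treatment estimate is about

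r = P - (s/b)[phi((c-b)/s) - phi((c+b)/s)], with P = Phi((c-b)/s) - Phi((-c-b)/s).

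For b = 0.4: P = 0.643 and r = 0.643 - (0.251/0.4)(0.373 - 0.001) = 0.41. For b = 0.2, r = 0.63; for b = 0.6, r = 0.18; for b = 1.0, r = 0.01. This ignores the 0.2 screen and the correlation between covariate and treatment.

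**4. Simulation (all strengths are assumptions).** 778 patients, residual SD 7, nine covariates: a baseline score at -3 points per SD, four confounders and four others. The confounders have treatment log-odds of 0.3 or 0.5 per SD and outcome effects of 0.2-0.6 points per SD. True effect 0, no missing data, 2,000 replicates. With all four acting in the same direction:

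| Log-odds | b | Unadjusted bias | r x unadjusted | Simulated bias, selected | 95% CI coverage |
|---|---|---|---|---|---|
| 0.3 | 0.2 | 0.23 | 0.15 | 0.16 | 93% |
| 0.3 | 0.4 | 0.43 | 0.18 | 0.21 | 92% |
| 0.3 | 0.6 | 0.65 | 0.12 | 0.15 | 93% |
| 0.5 | 0.2 | 0.32 | 0.20 | 0.22 | 92% |
| 0.5 | 0.4 | 0.66 | 0.27 | 0.32 | 86% |
| 0.5 | 0.6 | 0.97 | 0.18 | 0.24 | 88% |

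Over repeated runs the selected model gives 0.15-0.34 points of bias and 86-94% coverage. The full model gives at most 0.04 points.

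**5. Direction of confounding.** With one of the four reversed, the bias after selection is 0.06-0.15; with two reversed, at most 0.03. Coverage with mixed signs is about 90-95%, against about 94-97% for the full model.

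**6. Strength of confounding.** At 1.0 point per SD the bias after selection is 0.02-0.03, which is negligible.

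**7. Ten imputed data sets.** With 40% of eosinophil values missing and ten imputations, same-direction weak scenarios, 1.5-3.5 of the four confounders were dropped on average. The ten selected models were not all the same in 60-75% of runs.

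**8. Scale.** Against the 2-point CAT margin: 0.15/2 = 8% to 0.34/2 = 17%. For mMRC (SD 1, margin 1) at the same standardised strengths: 0.15/7 = 0.02 to 0.34/7 = 0.05 points.

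**The case against.** The case against giving this weight is good, and most of it stands.

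- The study is exploratory and matching is primary. Weighting already gives an adjusted check on the treated and per-protocol sets (SAP 7) without p-value selection.
- The size depends on assumed inputs. The upper figures need all confounders to act in the same direction, which nothing in the documents establishes. Other inputs move the figure up as well: nine weak confounders at 0.3-0.5 points per SD, with 30% missing in three covariates, gave 0.27-0.56 points, still below the margin.
- Removing selection would not make the approaches fully comparable. Matching uses a subset of the per-protocol set (SAP 6.3), regression uses the treated and per-protocol sets, and weighting targets the effect in the treated. Some differences would remain hard to attribute.

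A reader might also infer more than the text supports:

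- *That the regression certainly adjusts for a different set.* It need not: every term could survive.
- *That the SAP breaches the protocol.* Protocol 9.7.1 says which covariates adjustment includes, and Protocol 9.7 defers detail to the SAP. This is a weaker method within that latitude.
- *That the primary result is compromised.* The propensity score model keeps its list unless it fails to converge, so the matched analysis is untouched.

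What survives the objection is the mismatch itself and the interval coverage, which still falls when the bias cancels.

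**Conclusion.** The point holds as a low-priority improvement to a sensitivity analysis. The regression need not adjust for the covariates in the propensity score model or the protocol list, and its ten pooled estimates can come from different models.

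The harm is limited to weak confounders. In the settings examined it is a fraction of the CAT margin, small for mMRC, and close to nil when the confounders' directions balance. These sizes rest on assumed strengths, directions and independent covariates. The documents give no figures for any of them.

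**What to change.** In SAP 7.3, replace the univariate screen and backward elimination with one prespecified linear model for each primary outcome. It should contain treatment and all listed covariates, including the baseline score, in every imputed data set. Omit only levels that are empty in the analysis set: mMRC grade 0 and a positive exacerbation history may be empty in the per-protocol set, because the entry criteria rule them out. Pool the treatment coefficient by Rubin's rules and say so in place of the present wording on aggregation.

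The cost is SAP wording and programming, with no added patients or data. The downside is an SE about 1-9% larger for this regression in the weak-confounder scenarios and unchanged in the strong ones. In the same-direction weak scenarios without missing data, root mean squared error was still lower with the full model (0.52-0.56 against 0.55-0.67 with selection). That gain is not claimed when the signs are mixed.

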7.4 SECONDARY ENDPOINT(S)

Comparative analyses on secondary endpoints will be performed as for the main analysis but only the primary analytical approach (propensity score matching) will be employed. All secondary endpoint analyses will be done on the matched set. Additionally, the analysis based on data as collected (i.e. without applying any analytical approach) will be done using the treated set.

For general condition of patients according to the Physician’s Global Evaluation (PGE) and patient’s satisfaction with Spiolto® Respimat® as well as the proportion of responders ($\Delta_{\text{mMRC}} \geq 1$, $\Delta_{\text{CAT}} \geq 2$ respectively), the number and percentage of patients within each category will be displayed.

7.6 EXTENT OF EXPOSURE

Not applicable.

7.7 SAFETY ANALYSIS

The analysis of adverse events will be descriptive and conducted according to Boehringer Ingelheim standards. The main focus will be on treatment emergent events, i.e. events occurring after start of treatment (events after end of treatment are not documented). Non treatment-emergent events will be assigned to “screening” and only be displayed in listings. All analyses will be based on the treated set.

The frequency and severity of drug-related adverse events or events with fatal outcome (i.e., subset of serious adverse events) will be tabulated according to MedDRA-SOC and PT. Additionally adverse events (drug-related or serious ones) leading to treatment discontinuation will be presented. Moreover, the causality of events with fatal outcome will be displayed.

Unless otherwise specified, the analyses of drug-related adverse events and events with fatal outcome will be descriptive in nature. All analyses will be based on the number of patients with AEs and not on the number of events.

An overall summary of drug-related adverse events and events with fatal outcome will be presented.

The frequency of patients with drug-related adverse events or events with fatal outcome will be summarised by primary system organ class and preferred term. Separate tables will be provided for patients with serious adverse events.

The system organ classes will be sorted alphabetically, preferred terms will be sorted by frequency (within system organ class).

For analysis multiple AE occurrence data on the CRF will be collapsed into an AE event provided that all of the following applies:

- All AE attributes are identical (PT, NCI-CTC grade, action taken, therapy required, seriousness, reason for seriousness, relationship, outcome)
- The occurrences were time-overlapping or time-adjacent (time-adjacency of 2 occurrences is given if the second occurrence started on the same day or on the day after the end of the first occurrence). For classification into TEAE or Non-TEAE, the first documented start of event will be used.

For further details on summarization of AE data, please refer to [3] and [4].

10. HISTORY TABLE

Table 10: 1 History table

Version	Date (DD-MMM-YY)	Author	Sections changed	Brief description of change
Draft v0.1	12-JUN-2019		None	This is the first Draft-Version of TSAP without any modification
Draft v0.2	09-SEP-2019		2	Abbreviations completed
			5.1	Categorization of CAT™ added
			7.3	Revised
			7.4	Change in wording to explain issue more clearly
			7.7	Definition of TEAE added
Draft v0.3	18-SEP-2019		7.3	Revised
Draft v0.4	08-OCT-2019		7.3	Clarification of analysis for GOLD groups
Draft v0.5	19-FEB-2020		7.3	Number of primary outcomes corrected to three Clarification of multiple regression
Draft v0.6	26-MAY-2020		6.2	Header changed: deviation instead of violation
			6.3	Analysis of secondary endpoints for PP deleted Statement when PP analysis can be skipped added
			7.	Analysis of primary and secondary endpoints adapted
			7.3	p-values deleted Analysis on “data as collected” added Multivariable regression modeling adapted
			7.4	Analysis sets for secondary endpoints adapted Subgroup analyses deleted
Draft v0.7	17-JUL-2020		7.3	Definition of exacerbation history added
